7.1.2 Non-Date Values

Every effort will be made to obtain the protocol-required data for all study assessments that are scheduled for each scheduled visit for all subjects who have been enrolled. No data imputation will be applied to missing study data except for imputing visit dates to classify AE and concomitant medication data into the study phase of “pre-treatment,” “during treatment,” or “post-treatment.”

7.2 VISIT WINDOWS

All study data will be presented at the nominal visit obtained from the eCRFs, if available. Study day is defined as (date of visit – date of treatment initiation + 1). That is, study day 1 indicates the date of treatment initiation. In the case of early termination visit, date of the visit will be used to calculate the nominal visit for the analysis.

If there are two or more assessments within a nominal visit, then the assessment that is closest to the scheduled time point/target day will be used in the analysis. If there is more than one closest value, then the evaluation occurring after the target day and prior to the date of last dose will be used in the analysis.

All values will be included in the data listings.

7.3 DATA DERIVATIONS AND DEFINITIONS

General derivations that can be applied to any endpoint are defined below. For specific derivations that can only be applied to a particular endpoint, they will be defined in the section describing the endpoint.

Baseline Definition

Baseline measurement is defined as the last pre-treatment measurement obtained prior to the initial administration of BVD-523.

Change from Baseline

The change from baseline will be calculated by subtracting the baseline values from the individual post-procedure values. If either the baseline or post-procedure value is missing, the change from baseline is set to missing as well.

8 STUDY POPULATION

Unless otherwise stated, all study population analyses will be performed on the Safety Population.

8.1 SUBJECT DISPOSITION

The frequency and percentage of patients who receive at least one dose of BVD-523 or not, patients who have completed the study as per protocol or not, and patients who withdrew prematurely from the study with their reasons for discontinuation will be summarized by treatment group and overall (all treatment groups combined) for each study part². The total number of mITT patients in each treatment group for each study part will be used as the denominator for the calculation of percentages.

The number and percentage of patients in each of the five analysis populations as specified in Section 5 will also be tabulated similarly.

A listing of analysis population, study completion, and early termination with the primary reason for early withdrawal will also be provided.

8.2 DEMOGRAPHIC CHARACTERISTICS

Demographic and baseline characteristics will be summarized descriptively by treatment group and overall for each study part using the mITT and Safety Populations.

Demographic and baseline characteristics include, but are not limited to: age (years), age category (<65 and ≥65 years old), gender, ethnicity, race, weight (kg), height (cm), body mass index (BMI; kg/m²), Eastern Cooperative Oncology Group (ECOG) Performance Score, reproductive status, cancer type, tumor mutation status, type of scan (Echocardiogram or Multi-gated acquisition scan (MUGA)), left ventricular ejection fraction (LVEF) result, and molecular abnormalities when available.

Age will be calculated in years from date of birth to the date of informed consent as an integer value. BMI is calculated as $\text{weight} / (\text{height}/100)^2$, where weight is in kg and height is in cm.

² Part 1 and Part 2 use different categories. Part 1 categories are: Death, Anaphylaxis (angioedema, hypotension, shock, bronchospasm, hypoxia, or respiratory distress), Withdrawal of Informed Consent, Disease Progression, Unacceptable Toxicity, Change in the Subject's Condition that Renders the Subject Unacceptable for Further Treatment, At Least 3 Interruptions of BVD-523 Intake, Patient Becomes Pregnant, Patient is Lost to Follow-up, Other. Part 2 categories are: Withdrawal of Informed Consent, Disease Progression (at the discretion of the PI). However it is particularly important in patients for which FDA approved BRAF and/or MEK inhibitors are indicated that BVD-523 treatment NOT be continued beyond tumor progression, Unacceptable Toxicity, Changes in the Patient's Condition Render the Patient Unacceptable for Further Treatment in the Judgment of the PI, Patient Non-Compliance as Assessed by the Investigator, Patient has a Positive Serum Pregnancy Test (Withdrawal is Required), Patient is Lost to Follow-up, Other.

8.3 PRIOR AND CONCOMITANT MEDICATIONS

Medications will be coded according to the World Health Organization Drug Dictionary (WHO Drug, March 1, 2013). Summary of all medications will then be using the WHO Drug ATC classification and preferred term.

All medications taken, except for BVD-523, will be classified into prior or concomitant medications. A prior medication is defined as any medication taken within 28 days prior to the initiation of BVD-523 irrespective of whether it is continued into the study. A concomitant medication is defined as any medication taken after the initiation of BVD-523 and up to 30 calendar days after the last administration of BVD-523. If a medication falls into both prior and concomitant time phase then it will be presented in both time phases. All medications, except for BVD-523, will be summarized by WHO Drug ATC classification and preferred term with regards to treatment groups for each study part and time phase.

At each level (WHO Drug ATC classification and Preferred Term) of summarization, a subject will be counted only once per drug class or preferred term. For example, if a subject reports multiple concomitant medications with the same drug class, then that drug class will only be incremented by one. Similarly, if a subject reports multiple concomitant medications with the same preferred term, then that preferred term will only be incremented by one. Whether medications are taken for AEs or not will also be provided. The medication with indication equals to the AE verbatim which also has “Concomitant Medications” as the response to the question of “Any Treatment Required?” will be deemed as the medication taken for the AE. Medications taken for AEs will be tabulated by WHO Drug ATC classification and preferred term with regards to treatment groups for each study part.

Subject listing of medications will also be presented by time phase.

8.4 MEDICAL HISTORY

Medical history findings including change in medical condition since the last visit will be provided in a listing.

8.4.1 Previous Chemotherapy

Previous chemotherapy information includes description of the chemotherapy, start/stop date, reason for therapy, best response from the therapy, total number of cycles completed, prior anthracycline use, prior XRT use, and delivery site. They will be summarized by descriptive statistics by treatment group for each study part. Listing of previous chemotherapy information will also be provided in the order of occurrences within a patient.

8.4.2 Previous Immunotherapy

Previous immunotherapy data including type of immunotherapy (monoclonal antibodies, cancer vaccine, other immunotherapy), start/stop date, and reason for discontinuation (completed regimen, disease progression, other) will be listed by time of occurrence within a patient.

8.5 ON STUDY PROCEDURES

A listing of on study procedures including their purposes (prior medical condition, adverse event, other) will be provided.

8.6 INCLUSION/EXCLUSION CRITERIA

Inclusion and exclusion criteria failures will be included in a data listing.

8.7 TREATMENT COMPLIANCE

Patients will take BVD-523 orally twice daily for 21-day cycles until disease progression, unacceptable toxicity, or a clinical observation satisfying another withdrawal criterion is noted. Patients may be treated beyond disease progression for additional 21-day cycles at the Investigators discretion. However it is particularly important in patients for which FDA approved BRAF and/or MEK inhibitors are indicated that BVD-523 treatment NOT be continued beyond tumor progression. Treatment cycles will occur consecutively without interruption, except when necessary to manage toxicities. No intra-patient dose escalation was permitted under the original protocol or the first two amendments. Under amendment three, some intra-patient dose escalations were allowed. Under amendment four, intra-patient dose escalations are only allowed to bring subjects to the RP2D (after it is identified), if deemed medically appropriate and if the subject has not experienced any toxicity greater than Grade 1. Some intra-patient dose escalation may occur.

A listing of BVD-523 administration, dispensed, missed/interrupted dose, intra-patient dose escalations, returned, and compliance will also be provided.

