The classic 3 + 3 design will be conducted as follows. Initially, 3 patients will be enrolled to a cohort; the occurrence of a single drug-related DLT in one of these 3 patients will prompt enrollment of up to an additional 3 patients to that same cohort i.e., 3 + 3. When more than 1 DLT occurs in  $\leq$  6 patients in a dosing cohort, dose escalation will be stopped and this dose level will be identified as the non-tolerated dose. Doses between the non-tolerated dose and the preceding lower dose, where  $\leq$  1 DLT occurred, may be explored to define the MTD. This strategy allows for a rigorous determination of MTD, especially if the dose increase that resulted in determination of the non-tolerated dose is relatively large (i.e.,  $>$  50%).

At any time during the study, the Sponsor and Investigators may request that cohorts should be enlarged or that exploration of intermediate doses between 2 planned escalation steps should be explored. Such requests will be discussed with the Sponsor and Medical Monitor, and should be based on all data existing at that time, including determinations of pharmacokinetics, pharmacodynamics, and cumulative toxicity. Before each escalation, investigators will be consulted to ensure that all involved agree with the escalation decision.

In addition, once the RP2D is defined, intra-patient dose escalation to the RP2D will be allowed after a patient has completed at least 1 cycle at their assigned dose and only if the patient has experienced no toxicity above Grade 1, upon request by the PI and discussion with the Medical Monitor and the Sponsor.

Part 2 – Cohort-expansion Phase: Additional patients with particular tumor types and/or cancers harboring specific genetics will be recruited for treatment at the Recommended Phase 2 Dose (RP2D). Patients must have measurable disease by RECIST 1.1. Patients will receive twice daily oral doses of BVD-523 in 21-day treatment cycles until disease progression, unacceptable toxicity, or another withdrawal criterion is met (Section 7.2). Treatment cycles will occur consecutively without interruption except when necessary to manage toxicities.

Total enrollment for Part 2 is targeted at approximately 105 evaluable patients. Patients will be enrolled into 1 of 7 treatment groups. Group assignments are made according to the following disease characteristics, which correspond to specific inclusion and exclusion criteria for Part 2.

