### 10.3.6 Secondary Endpoints

#### Anti-tumor Activity as Evaluated Using RECIST Criteria

Disease response will be summarized in tabular format showing the number and percent of patients in each dose level.

No formal efficacy analysis will be conducted.

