2.2 TREATMENT GROUPS

Treatment groups of the study consist of various dose level cohorts (starting at 10 mg twice daily (bid) for 21 days (a “Cycle”)) used in the dose-escalation phase of the study and the group number (Group 1 - Group 7 as specified in Section **Error! Reference source not found.**) used in the cohort expansion phase of the study and dosed at the RP2D.

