3 STUDY DESIGN

3.1 OVERALL STUDY DESIGN

This is an open-label, multi-center Phase 1 study to assess the safety, pharmacokinetics, and pharmacodynamics of escalating doses of BVD-523 in patients with advanced malignancies. It will be conducted at up to 15 sites. This clinical study comprises 2 parts: Part 1: Dose-escalation Phase and Part 2: Cohort Expansion Phase.

Part 1: Dose-escalation Phase, An accelerated dose escalation plan will be used to establish DLT, MTD, and the RP2D. One to 6 patients per treatment cohort will be assigned to receive sequentially higher oral doses of BVD-523 on a twice daily schedule (b.i.d.) for 21 days (a “Cycle”), starting at a dose of 10 mg twice daily. Patients will receive twice-daily oral doses of BVD-523 until disease progression, unacceptable toxicity, or a clinical observation satisfying another withdrawal criterion is noted. Treatment cycles will occur consecutively without interruption, except when necessary to manage toxicities. Up to 40 patients will be enrolled in Part 1. Patients with advanced-stage solid tumors only (no hematological malignancies) will be enrolled in the dose-escalation phase of the study. The study will initially be conducted as an accelerated single patient cohorts design, followed by a standard 3 + 3 design, informed by the accrued safety experience throughout the study (see Table 1 below). All dose-escalation decisions will be based on Cycle 1 safety data. Patients who withdraw at any time preceding the last visit of Cycle 1 (Day 22) will constitute an early discontinuation and must be replaced in order to ensure proper data accrual for dose escalation decisions. A patient who experiences a DLT in Course 1 and withdraws before Day 22 either because of the toxicity or otherwise, will nonetheless have that DLT counted in the assessment of potential cohort expansion and/or dose escalation. Doses will not be escalated unless the patient(s) receiving the highest current dose has been observed for at least 3 weeks. No intra-patient dose escalation was permitted under the original protocol or the first two amendments. Starting under amendment three, intra-patient dose escalations were allowed; see protocol for details.

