- \geq Grade 3 non-hematologic toxicity, except untreated nausea, vomiting, constipation, pain, and rash (these become DLTs if the AE persists despite adequate treatment), a doubling of AST/ALT in patients with grade 2 ALT/AST at baseline;
- A treatment interruption exceeding 5 days (or an interruption exceeding 7 days for rash, despite adequate treatment) in Cycle 1 (or inability to begin Cycle 2 for > 7 days) due to BVD-523-related toxicity³.

As specified in Section 2.1.1, the MTD is defined as the highest dose level at which $\leq 33\%$ of patients experience BVD-523 related DLTs in the first 21 days of treatment. The RP2D may be as high as the MTD and will be determined in discussion with the Clinical Investigators, the Medical Monitor, and the Sponsor. Observations related to pharmacokinetics (PK), pharmacodynamics (PD), and any cumulative toxicity observed after multiple cycles may be included in the rationale supporting the RP2D. Pharmacokinetic, pharmacodynamics, and/or Holter measurements may be suspended pending review of accumulated patient experience.

Treatment Emergent Adverse Event

A treatment emergent adverse event (TEAE) is any AE temporally associated with the use of BVD-523 (from BVD-523 initiation until 30 calendar days after the last administration of BVD-523), whether or not considered related to the study drug. If the onset of an AE is missing and the AE resolution date is either after the initial BVD-523 dose date or missing, then the AE will be considered treatment emergent.

AE Summaries

A subject who reported multiple AEs that map to a common PT or SOC is counted only once for that PT or SOC at the highest severity reported and at the greatest relationship to study drug.

The number and percentage of subjects who experienced at least one AE will be tabulated by SOC and PT with respect to dose level/treatment group for each study part. The same tabulation will also be applied to any SAE, any AE leading to premature discontinuation from the study, treatment emergent AEs and treatment-emergent SAEs.

³ For Amendments 1 and 2: A treatment interruption exceeding 3 days in Cycle 1 due to drug-related toxicity (or inability to begin Cycle 2 for > 7 days) due to drug-related toxicity.

For Amendment 3: A treatment interruption exceeding 5 days in Cycle 1 due to drug-related toxicity (or inability to begin Cycle 2 for > 7 days due to drug-related AE)

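### Part 1 AE and response tables have no rule for events after intra-patient escalation, so read as written they count those events in the starting-dose column

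*SAP*

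**What the plan says.** - **Grouping.** SAP 2.2: "Treatment groups of the study consist of various dose level cohorts" in Part 1, and Groups 1 to 7 in Part 2. Cohort membership is set at entry. SAP 3.1: "One to 6 patients per treatment cohort will be assigned to receive sequentially higher oral doses of BVD-523". The same section gives the first cohort's dose: "starting at a dose of 10 mg twice daily".
- **Dose changes.** SAP 3.1: "Starting under amendment three, intra-patient dose escalations were allowed". SAP 8.7 adds that from Amendment 4 escalation goes only to the RP2D, once that is identified, and closes with "Some intra-patient dose escalation may occur". Protocol 3.1.2 sets the current terms: "intra-patient dose escalation to the RP2D will be allowed after a patient has completed at least 1 cycle at their assigned dose". It adds the condition that toxicity up to then was no worse than Grade 1.
- **AE tables.** SAP 10.2: patients with an AE "will be tabulated by SOC and PT with respect to dose level/treatment group for each study part". Each patient counts once per term, at the worst grade. The treatment-emergent window runs from first dose to 30 days after the last dose.
- **Response tables.** SAP 9 uses study part, dose level/treatment group and visit. Protocol 10.3.6 plans a table "showing the number and percent of patients in each dose level".
- **Where escalations appear.** Only in listings: the administration listing in SAP 8.7 and the Dose History listing (16.2.1.10.3) in SAP 14.

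**The concern.** A by-dose table is read as what happened at each dose. Here the column is fixed at entry, the event window covers all time on drug, and the dose may rise in between. Neither document assigns an AE to the dose at onset, cuts data at escalation, or gives escalated patients their own column.

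Two features add to the problem. Part 1 columns are very small, so one patient matters. And the escalation condition interacts with worst-grade counting: a patient eligible under the current rule has had only Grade 1 toxicity at the starting dose, so anything worse arises later but is the grade the table shows.

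At stake are the Part 1 AE tables, where treatment-related AEs are a primary endpoint (Protocol 3.5.1, SAP 2.3.1), the Part 1 response tables, and later use of cumulative toxicity by dose, which Protocol 3.1.3 and 8.1.2 say may affect the RP2D.

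**Working it through.** The plan states no figure that depends on this point, so there is none to reproduce. The check is to follow the rules for one patient and then size the effect.

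**Following the rules**

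1. A patient enters a low cohort. By SAP 2.2 that cohort is the patient's treatment group.
2. After at least one cycle, with toxicity no worse than Grade 1, the patient is escalated to the RP2D.
3. A Grade 3 related AE follows. It lies inside the treatment-emergent window and is the worst grade for its term.
4. SAP 10.2 counts it once, at Grade 3, by dose level/treatment group. Read with SAP 2.2, that is the low cohort, where the patient never had this grade.
5. Response works the same way. Escalation is possible after one cycle, but the first planned tumor evaluation is at the end of Cycle 2 (SAP 9). A patient could be escalated before any response is measured and still be shown only under the starting cohort.
6. DLTs are limited to the first 21 days, and current escalation needs a completed 21-day cycle. DLT and MTD tables are therefore untouched under the current rule.

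**Size for one patient**

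If the patient would not otherwise be counted in that row, the column rate moves by 1/n. Cohorts hold 1 to 6 patients (SAP 3.1):

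- n = 1: 1/1 = 100 points
- n = 3: 1/3 = 33 points
- n = 6: 1/6 = 17 points

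**Illustration under assumed values**

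The documents give neither the number escalated nor the risks. Let p be the AE risk at the starting dose, e the share of patients without the event there who are escalated, and q their AE risk afterwards. All three are assumptions.

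Apparent rate = p + (1 − p) × e × q

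| p | e = 0.10, q = 0.30 | e = 0.67, q = 0.67 |
|---|---|---|
| 0.05 | 0.05 + 0.95 × 0.030 = 0.079 | 0.05 + 0.95 × 0.449 = 0.476 |
| 0.20 | 0.20 + 0.80 × 0.030 = 0.224 | 0.20 + 0.80 × 0.449 = 0.559 |

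Now take e as a share of the whole cohort, with patients independent. The chance that a cohort carries at least one post-escalation event is 1 − (1 − e × q)^n. Over the same range it is 3% to 45% for n = 1, 9% to 83% for n = 3, and 17% to 97% for n = 6. The width of these ranges shows that the actual size cannot be told from the plan.

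**The case against.** A reader might infer that the evidence behind the RP2D is distorted. The documents mostly rule this out. Escalation to the RP2D comes only after it is defined, dose-escalation decisions rest on Cycle 1, and the Part 1 analysis in SAP 12 is meant to inform the choice of MTD and RP2D. Only Amendment 3 escalations could come earlier, and their rules and number are not in these documents.

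A reader might also infer that experience at the RP2D is seriously under-counted. Part 2 plans about 105 patients at that dose, so a few escalated Part 1 patients add little.

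Other points carry weight:

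- The SAP never says that columns use the assigned dose. SAP 6.6 lists dose level and cohort/treatment group as separate sort keys, and the table shells are stand-alone documents, so column footnotes cannot be checked. The cohort reading follows from SAP 2.2 and the absence of any other rule. If the term is ambiguous, two programmers could build different tables, and the same sentence would settle it.
- The 100-point shift is a worst case. It needs a patient from a single-patient cohort who is still on drug and eligible when the RP2D is defined. A one-patient column says little anyway.
- With about 40 Part 1 patients, events can be traced by hand through the listings, and no inferential testing is planned. That softens the problem but does not correct the summary tables.
- Moving every event to the dose at onset has its own faults: it needs a denominator for each dose, and escalated patients are selected for tolerating the drug. Crediting a response only to the dose at the time ignores earlier dosing, since RECIST response is measured from the pre-treatment baseline. This argues for a different fix, not for silence.

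**Conclusion.** The point holds as a gap in the rules for the Part 1 by-dose tables. Read with SAP 2.2, AEs and responses after escalation are counted at the starting dose. For patients escalated to the RP2D under the current rule, this covers every toxicity of Grade 2 or higher. If AE risk and activity rise with dose, lower cohorts will look more toxic and more active than they were.

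The effect is 100, 33 or 17 points per affected patient for n = 1, 3 or 6; the total is unknown because the number escalated is not given. DLT and MTD results stand under the current rule, and the initial RP2D choice is largely unaffected. Neither can be confirmed for patients escalated under Amendment 3. A claim that RP2D selection was biased would go beyond the documents. This is a cheap improvement to reporting and to any later review of cumulative toxicity by dose.

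**What to change.** In SAP 10.2, keep the starting-cohort columns, but cut each Part 1 patient's AE data at the first intra-patient escalation. Show AEs with onset after that in a separate post-escalation column whose denominator is the number of patients escalated. Apply the once-per-term, worst-grade rule within each column.

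In SAP 9, keep responses under the starting cohort, flag escalated patients, and show the dose being taken at first response.

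Report the number of patients escalated per cohort.

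The dosing inputs are already planned for Listing 16.2.1.10.3, so no new data and no change to patient care are needed. The cost is SAP wording and some programming. Escalated patients will appear in two AE columns, so column counts no longer add up to the Part 1 total; a footnote should say so.
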